7.23.5.2 Eliciting Adverse Events

Patients should be asked non-leading questions (eg, “How do you feel?”) and further questions should be posed if there is indication of an AE. The questioning should be conducted with due regard for objectivity and, in particular, the questioner should gather information regarding AEs from questioning the patient, the patient’s parent/guardian, spontaneous report by the patient or parent/guardian, laboratory reports, and any health care provider’s observations.

The onset date, resolution date, treatment administered, and outcome of each AE must be recorded on the appropriate eCRF. The relationship of each AE to study medication must be recorded. In addition AEs may be considered to be related to the IDDD, the IDDD surgical procedure, or the IT administration process. Since the AE may be deemed to be related to more than one of these factors, as many of these IDDD-related options as apply should be indicated on the eCRF.

7.23.5.3 Protocol Deviations for Medical Emergency or Adverse Event

During and following a patient’s participation in the study, the Investigator should ensure that adequate medical care is provided to a patient for any AEs, including clinically significant laboratory test results.

The Investigator should inform the patient, the patient’s parent(s), or the patient’s legally authorized representative when medical care is needed for intercurrent illness(es) of which the Investigator becomes aware. In an emergency situation, the Investigator should contact the Shire HGT Medical Monitor (see Section 7.23.5.1).

Only when an emergency occurs that requires an immediate deviation from the protocol for the safety of a patient, will there be such a deviation and this will be only for that patient.

The Investigator or other physician in attendance in such an emergency must contact the Shire HGT Medical Monitor as soon as possible.

The Investigator, along with the Shire HGT Medical Monitor, will make a decision as to whether or not the patient should continue in the study prior to the next scheduled dose. The departure from the protocol and the grounds for it should be stated in the eCRF.

7.24 Abuse, Overdose and Medication Errors

Abuse, misuse, overdose or medication error must be reported to the Sponsor according to the SAE reporting procedure whether or not they result in an AE/SAE as described in Section 7.23.

- **Abuse** – Persistent or sporadic intentional intake of investigational medicinal product at a dose higher than prescribed per protocol (but below the dose defined for overdose) or when used for non-medical purpose (eg, altering one’s state of consciousness)
- **Misuse** – Intentional or unintentional use of investigational medicinal product other than as directed or indicated at any dose, which is at or below the dose defined for overdose (Note: This includes a situation where the test article is not used as directed at the dose prescribed **by the protocol**)
- **Overdose** – Overdosage with adverse clinical consequences is not anticipated with the use of HGT-1410. Additionally, HGT-1410 will be given in a clinical setting by a health care provider.
- **Medication Error** – A mistake made in prescribing, dispensing, administration and/or use of the investigational medicinal product.

7.25 Safety-related Study Stopping Rules

If any patient experiences a life-threatening (Grade 4) adverse event or death which is considered by the sponsor to be possibly, probably, or definitely related to study drug **or the IDDD**, or if 2 or more patients experience a Grade 3 adverse event during the trial that is considered by the sponsor to be possibly, probably, or definitely related to the study drug **or the IDDD**, then the site will be instructed to halt further HGT-1410 administration to all patients and the safety data reviewed. Following a review of safety data, the study will be either:

- Resumed unchanged
- Resumed with modifications to the protocol or
- Terminated

Patient safety will be monitored on a continuous basis during this study until the last patient completes his or her last scheduled study visit/assessment.

7.26 Pregnancy

Pregnancy and breast feeding are exclusion criteria. Only female patients who have reached menarche will be tested for pregnancy in HGT-SAN-067. If applicable, this will occur at study start and before each dose of HGT-1410 throughout the study. Pregnancy testing will be performed on a blood or urine sample. Patients with a positive or inconclusive result will not be eligible for this study.

At study start, a pregnancy test will be performed if more than 30 days have passed since the initial screening sample. Throughout the study pregnancy testing will occur prior to each dose of HGT-1410. The clinical site’s local laboratory will analyze and report all pregnancy testing results. If a pregnancy test is positive the patient will be discontinued from the study, and the Investigator must contact the Shire HGT Medical Monitor.

Pregnancy is not to be reported as an AE; the Pregnancy Reporting Form, found in the Study Operations Manual along with instructions for completion, should be used to report the pregnancy. The pregnancy will be followed up through delivery or final outcome.

7.27 Removal of Patients from the Trial or Study Drug

The patient's parent or legally authorized representative acting on behalf of the patient is free to withdraw consent and discontinue participation in the study at any time without prejudice to further treatment. Since this is an extension trial, there will be no replacement of patients who discontinue the study for any reason.

A patient's participation in the study may be discontinued at any time at the discretion of the Investigator, Sponsor, or Medical Monitor. The following may be justifiable reasons for the Investigator, Sponsor, or Medical Monitor to remove a patient from the study:

- Adverse Event: If a patient experiences an AE which, in the judgment of the investigator, the sponsor, or the medical monitor, presents an unacceptable consequence or risk to the patient.
- Adverse Laboratory Experience: If a patient has an adverse laboratory experience which, in the judgment of the investigator, the Sponsor, or the medical monitor, presents an unacceptable consequence or risk to the patient, the patient may be withdrawn from the study.
- Comorbidity: If a patient develops comorbidity during the course of the study that is independent of the study indication, and treatment is required that is not consistent with protocol requirements.
- Intercurrent Illness: If a patient develops an illness during the course of the study that is not associated with the condition under study, and which requires treatment that is not consistent with protocol requirements.
- Refusal of Treatment: If the patient, the patient's parent(s) or legally authorized representative(s) discontinues participation in the study, or the patient is discontinued by the Investigator, reasonable efforts will be made to follow the patient through the end of study assessments. The reason for refusal will be documented on the eCRF.
- Withdrawal of Informed Consent: A patient's parent or legally authorized representative may withdraw his informed consent to participate in the study at any time.
- Cerebrospinal fluid leukocyte count >100 cells per cubic millimeter for 2 consecutive months.
- New onset seizure.
- Anaphylactic reaction beyond reasonable management as described in the Investigator's Brochure.
- Clinically problematic intubations or extubations, which may preclude safe airway management and anesthesia.
- Development of refractory spinal fluid leakage.
- Clinically significant prolonged (eg, greater than 24 to 48 hours) worsening in mental status, including development of new focal or non-focal neurological symptoms, or recurrence of a previously stable prior medical problem judged due to study drug or participation that is exclusive of effects from anesthesia.
- Non-compliance, including failure to appear at 1 or more study visits.

- The patient was erroneously included in the study.
- The patient develops an exclusion criterion.
- The study is terminated by the Sponsor.
- The patient becomes pregnant during the trial.

If a patient discontinues the study the Patient Completion/Discontinuation eCRF describing the reason for discontinuation must be completed. Any AE's experienced up to the point of discontinuation must be documented on the AE eCRF.

If AEs are present when the patient withdraws from the study, the patient will be re-evaluated within 30 days of withdrawal. All ongoing SAEs at the time of withdrawal will be followed until resolution.

At the time of discontinuation or withdrawal, patients will be asked to participate in all safety and efficacy evaluations required for the end of study visit and for the safety follow-up visit. Participation in these EOS procedures will be strongly encouraged, but is voluntary for those patients electing to discontinue from the study. The patient will be scheduled for the removal of the IDDD.

7.28 Other Study Procedures

This section is not applicable.

7.29 Appropriateness of Measurements

The neurocognitive and developmental assessments are intended to gauge which domains can be accurately measured, with which specific tools, despite the considerable behavioral and cognitive challenges in Sanfilippo syndrome. The evaluation of these domains and the analysis of CSF, serum, and urine biomarkers may provide the pivotal data necessary to inform the clinical assessments and biomarkers used in possible future Sanfilippo syndrome ERT trials.

8 STUDY ACTIVITIES

Patients who participated in Study HGT-SAN-055 through Week 26 and completed the EOS evaluations may be eligible for enrollment in this open-label extension study. Informed consent (and assent, if applicable) must be obtained prior to performing any study related procedures that are specific to HGT-SAN-067. Informed consent may be obtained anytime from Week 20 in HGT-SAN-055. This would allow a patient to have a nonfunctional IDDD replaced or revised prior to the first HGT-1410 dose in HGT-SAN-067.

8.1 Screening Visit/Study Start Visit

All Screening assessments for this study are to have been performed during the Week 26 EOS procedures in HGT-SAN-055 (ie, 30 [\pm 7] days after the last HGT-1410 administration). If less than 60 days have elapsed since completion of the EOS assessments for HGT-SAN-055, and the start of HGT-SAN-067, the assessments detailed in this Screening visit do not need to be repeated. The Baseline visit for this study will be the first day the patient received their first dose of HGT-1410 in the HGT-SAN-055 Study.

If more than 60 days have elapsed following the HGT-SAN-055 EOS procedures, patients will be evaluated for enrollment in HGT-SAN-067 on a case-by-case basis by the Investigator. A decision about enrollment will be made following discussion with the Medical Monitor. If the patient is enrolled, the following assessments are to be repeated within 30 days prior to the first scheduled intrathecal HGT-1410 dose:

- Physical examination
- Height and weight
- Head circumference
- ECG
- Vital signs
- Hematology
- Leukocyte pellet preparation to be used for additional disease-related laboratory studies, including possible assessment of cross-reactive immunologic material (if this is not collected at baseline, it can be collected at any subsequent pre-dosing time point)
- Serum chemistry
- Pregnancy testing (for post menarche premenopausal females only)
- Urinalysis
- Urine heparan sulfate and heparan sulfate derivatives
- Plasma and serum heparan sulfate and heparan sulfate derivatives
- Anti-rhHNS antibody testing
- General anesthesia: administration of anesthesia will be given prior to the following assessments:
 - ABR
 - MRI of the head
 - Neurological examination (performed prior to the administration of anesthesia)

- Full Neurodevelopmental assessments, including Vineland Adaptive Behavior Scales, Second Edition (VABS-II; all assessments performed prior to the administration of anesthesia)
- CSF sample collection (chemistry, cell count, heparan sulfate and heparan sulfate derivatives, and other MPS exploratory biomarkers) via the IDDD
- Children's Sleep Habits Rating Scale
- CHQ-50
- CHQ-87
- ITQOL
- Concomitant medications, therapies, and procedures
- AE assessments

8.2 Treatment: Drug Administration and Weekly Assessments

Patients will receive HGT-1410 IDDD monthly (Q4W), on Day 2 (± 2 days), Week 1.

Patient assessments for safety, biochemical, and neurological baseline measures (Day 1, Week 1) will occur on the day before the first IT injection. Note: Day 1 assessments may be performed on the same day as the administration of study drug (Day 2). This can occur if it is feasible for the patient to arrive at the study site early in the day, and if it is deemed clinically appropriate by the Investigator. If the procedures on Day 1 and Day 2 are combined in this way, the assessments will be recorded as occurring on Day 2.

CSF samples will be obtained from these patients on Day 2, immediately prior to the first IT study drug injection.

8.2.1 Week 1

8.2.1.1 Day 1 (Pre-treatment) Assessments Performed Prior to Each Dose

- Physical examination
- Height and weight
- Vital signs
- Hematology
- Serum chemistry
- Urinalysis
- Pregnancy testing (applicable females only)
- Neurological examination (performed prior to the administration of anesthesia and the HGT-1410 IT injection)
- Concomitant medications, therapies, and procedures
- AE assessments

Note: If the HGT-SAN-055 EOS (or HGT-SAN-067 Screening) assessments were performed within 7 days of first intrathecal HGT-1410 treatment in this study, the pre-treatment assessments described in this section do not need to be completed prior to the first treatment in study HGT-SAN-067.

DAY 1 (PRE-TREATMENT) ADDITIONAL ASSESSMENTS PERFORMED AT MONTHS 12, 24, 36, AND 54

- Head circumference
- Visual and hearing assessments
- Urine heparan sulfate and heparan sulfate derivatives
- Plasma and /or serum heparan sulfate and heparan sulfate derivatives
- Anti-rhHNS antibody testing
- ABR
- MRI of the head
- Full neurodevelopmental testing, including VABS-II (performed prior to the administration of anesthesia and the HGT-1410 IT injection)
- Children's Sleep Habits Rating Scale
- Child health questionnaire-50
- Child health questionnaire-87
- Infant toddler QoL Questionnaire

8.2.1.2 Day 2 (± 2 days) Assessments and Administration of HGT-1410

Patients may be discharged from the clinical site 4 hours after dosing, if deemed stable by the Investigator.

- Physical examination
- ECG (performed following IT study drug injection)
- Vital signs
- CSF sample collection (obtained prior to IT study drug injection)
- HGT-1410 IT injection (Day 2 ± 2 days)
- Neurological examination
- Concomitant medications, therapies, and procedures
- AE assessments

The neurological exam should not occur sooner than 4 hours after study drug administration or before the patient has fully recovered from any anesthesia administered for the dosing, whichever occurs later.

8.3 End of Study/Early Termination Procedures: Month 55

Patients who complete the study or who discontinue prior to the end of the study, will have EOS assessments performed 30 (± 7 days) after their last dose of HGT-1410.

Patients who discontinue or are withdrawn prior to study completion will be asked to participate in the EOS procedures at the time of discontinuation. Participation in these EOS procedures will be strongly encouraged, but is voluntary for those patients electing to discontinue from the study. Note: Patients will have the IDDD removed when they discontinue from the study, unless the patient is continuing to receive treatment through another mechanism (eg, expanded access, commercially available).

- Physical examination
- Height and weight
- Head circumference
- Visual and hearing assessment
- ECG
- Vital signs
- Hematology
- Serum chemistries
- Urinalysis
- Urine heparan sulfate and heparan sulfate derivatives
- Plasma and serum heparan sulfate and heparan sulfate derivatives
- Anti-rhHNS antibody testing
- ABR (unless performed at Month 54)
- MRI of the head (unless performed at Month 54)
- CSF sample collection (unless performed at Month 54)
- Neurological examination
- Full neurodevelopmental testing, including VABS-II
- Children's Sleep Habits Rating Scale
- Child health questionnaire-50
- Child health questionnaire-87
- Infant toddler QoL Questionnaire
- Concomitant medications, therapies, and procedures
- AE assessments
- X-ray of device, if the patient is to continue to receive intrathecal HGT-1410 beyond the end of the study

All patients who discontinue the study early will have their IDDD removed.

Patients who withdraw or discontinue after having received fewer than 3 IT injections will not need to complete the EOS visit.

Patients who withdraw or discontinue from the study after having received 3 or more IT injections, will be asked to complete the EOS visit and undergo all the scheduled assessments.

8.4 Safety Follow-up (by Telephone or Visit) Month 56

Patients who complete the study or withdraw early will have a safety follow-up telephone call or visit 30 Days (± 7 days) after the last study visit. This will assess:

- Concomitant medications, therapies, and procedures
- AE assessments

9 QUALITY CONTROL AND ASSURANCE

Training will occur at an investigator meeting or at the site initiation visit or both, and instruction manuals (eg, laboratory manuals and pharmacy manuals) will be provided to aid consistency in data collection and reporting across sites.

Clinical sites will be monitored by Shire HGT or its designee to ensure the accuracy of data against source documents. The required data will be captured in a validated clinical data management system that is compliant with the Food and Drug Administration (FDA) 21 Code of Federal Regulations (CFR) Part 11 Guidance. The clinical trial database will include an audit trail to document any evidence of data processing or activity on each data field by each user. Users will be trained and given restricted access, based on their role in the study, through a password protected environment.

Data entered in the system will be reviewed manually for validity and completeness against the source documents by a clinical monitor from Shire HGT or its designee. If necessary, the study site will be contacted for corrections or clarifications; all missing data will be accounted for.

SAE information captured in the clinical trial database will be reconciled with the information captured in the Pharmacovigilance database.

10 PLANNED STATISTICAL METHODS

10.1 General Statistical Methodology

This is an open-label extension of study HGT-SAN-055 to evaluate the long-term safety and clinical outcomes of intrathecal administration of HGT-1410 in patients with MPS IIIA. The statistical methodology supporting the trial will focus on descriptive rather than inferential approaches, given the early phase and objectives of this trial.

Data will be summarized by dose group (10 mg, 45 mg, and 90 mg) with respect to demographic and baseline characteristics, efficacy variables, and safety variables. Summary statistics for continuous variables will include the n, mean, standard deviation, median, minimum and maximum. Categorical variables will be summarized in a contingency table by the frequency and percentage of patients in each category. Data will be plotted to assess trends across time as appropriate.

No a priori hypotheses will be tested. Exploratory hypotheses may emerge from the data analysis, in which case, appropriate testing methods will be applied and specified in the statistical analysis plan.

There are no formal hypotheses associated with the evaluation of the safety and performance of the IDDD device (SOPH-A-PORT Mini S). All analyses of device safety and performance will be descriptive and no statistical testing will be performed. Device related analyses will be based on patients for whom the device implant procedure was performed and are described in the sections below.

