14. The patient has received a hematopoietic stem cell or bone marrow transplant.

For patients to be implanted with the SOPH-A-PORT Mini S IDDD the following conditions are contraindicated, as described in the Instructions for Use:

1. The patient has had, or may have, an allergic reaction to the materials of construction of the SOPH-A-PORT Mini S device
1. The patient's body size is too small to support the size of the SOPH-A-PORT Mini S Access Port, as judged by the Investigator
1. The patient has a known or suspected local or general infection
1. The patient is at risk of abnormal bleeding due to a medical condition or therapy
1. The patient has one or more spinal abnormalities that could complicate safe implantation or fixation
1. The patient has a functioning CSF shunt device
1. The patient has shown an intolerance to an implanted device

Duration of Treatment:

The study duration will be 4 years.

Pharmacokinetic Variables:

N/A.

Safety Assessments:

Safety evaluations will include vital signs, physical examinations, AE assessments, electrocardiograms (ECG); serum chemistry, hematology, urine laboratory tests, and screening for antibodies to rhHNS (in CSF and serum).

Statistical Methods: The statistical methodology supporting the trial will focus on descriptive rather than inferential approaches, given the early phase and objectives of the trial. Data will be plotted and the mean, standard deviation, median, minimum, and maximum for each variable will be tabulated by dose group to look for gross trends over time, which may be attributed to treatment. For continuous data, 95% confidence interval (CI) around the mean will also be estimated and presented.

The analysis population consists of all eligible patients from HGT-SAN-055 who have completed Study HGT-SAN-055 and agreed to participate in this extension study. Safety analyses will be performed using the above mentioned population. The data will be presented by dose group.

Date of Original Protocol: 21 June 2010

Date of Amendment 5: 17 January 2014

LIST OF ABBREVIATIONS AND DEFINITIONS OF TERMS

Abbreviation	Definition
ABR	auditory brainstem response
AE	adverse event
ALB	albumin
ALK-P	alkaline phosphatase
ALT	alanine aminotransferase (SGPT)
AST	aspartate aminotransferase (SGOT)
βhCG	human chorionic gonadotropin
BSID-III	Bayley Scales of Infant Development, Third Edition
BBB	blood brain barrier
BUN	blood urea nitrogen
Ca	calcium
CE	Conformité Européenne
CFR	Code of Federal Regulations

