1 INTRODUCTION

The progressive and irreversible nature of lysosomal storage diseases (LSDs) present a challenge in the interpretation of clinical benefit derived from treatment in studies using enzyme replacement therapy (ERT). Any short-term improvement and/or stabilization of clinically important manifestations of the disease may be viewed as clinically meaningful. However, the demonstration of the different aspects of a long-term, clinically-meaningful improvement may be limited by the short duration of treatment in clinical studies. Extended access to treatment through extension studies provides an opportunity for further evaluation of long-term safety and clinical outcomes for treated patients. In this extension study, patients who completed study HGT-SAN-055, a phase I/II safety and dose-escalation trial, and elected to continue to receive recombinant human heparan N-sulfatase (rhHNS), will receive treatment through this extension protocol. Initially, the patient's treatment group and dosing regimen will be the same as that employed in study HGT-SAN-055. Following the analysis of data from HGT-SAN-055, patients in the lowest dose group will have their dose increased to 45 mg, as outlined in Section 1.3, below.

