6.4 Method of Assigning Patients to Treatment Groups

This is an open-label, non-randomized study; all patients enrolled in this study will be treated with HGT-1410. Patients will initially receive the same dose of HGT-1410 they received in Study HGT-SAN-055. Patients assigned to Group 1 (10 mg once per month [Q4W]) will have their dose increased to 45 mg once per month (Q4W) at the first administration of HGT-1410 following full approval of protocol Amendment 4.

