10.6 Efficacy, Safety, and Pharmacodynamic Evaluations

10.6.1 Primary Analyses

10.6.1.1 Safety Analysis

In general, safety assessments will be based on all assessments post-baseline. The assessment of safety will be based primarily on the frequency of AEs, and on the frequency of clinically notable abnormal vital sign and laboratory values. Changes from baseline will be calculated by subtracting the baseline value from the post-baseline value.

All enrolled patients who had an IDDD surgical procedure and/or received administration of HGT-1410 will be included in the safety analysis.

Adverse events will be recorded throughout the study and at early termination. Adverse events and medical conditions will be coded using the Medical Dictionary for Regulatory Activities (MedDRA).

Adverse events will be summarized by presenting, for each dose group, the number and percentage of patients having any AE, having an AE in system organ class, and having each individual AE. In addition, those events which resulted in death or were otherwise classified as serious will be presented in a separate listing. The incidence of treatment-emergent adverse events, defined as all AEs from the time of the surgery for IDDD implantation to the last follow up contact, ie, 30 days after the last HGT-1410 administration, (new or worsened from baseline) will be summarized by system organ class, severity, type of adverse event and relationship to trial medication/procedure.

Treatment-emergent AEs deemed related to HGT-1410 administration will be summarized separately.

IDDD, and procedure-related AEs will be summarized within system organ class by preferred term. IDDD and procedure-related AEs will be tabulated by severity (mild, moderate, severe) and degree of relatedness. Separate tabulations will be provided for adverse events related to the IDDD, device surgical procedure (including post-implant infections) and IT administration process. These summaries will be presented by device and overall, as appropriate.

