10.6.3 Secondary Analysis

10.6.3.1 Clinical Assessments

The change from baseline in neurocognitive assessment based scores will be examined by dose group. Furthermore, the effect of HGT-1410 administration on QoL measures will be examined by presenting mean change from baseline by dose groups. Other relevant assessments which might help in the understanding of clinical activity will also be analyzed.

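### Section 10 keeps fixed 10, 45 and 90 mg summary columns although Group 1 moves from 10 to 45 mg during the study, so results arising on 45 mg are reported under 10 mg

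*Protocol*

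**What the plan says.** The current version is Amendment 5 of 17 January 2014. Section 10.1 fixes the layout: "Data will be summarized by dose group (10 mg, 45 mg, and 90 mg) with respect to demographic and baseline characteristics, efficacy variables". It adds safety variables to that list. The synopsis, under Statistical Methods, makes the same commitment: summary statistics "for each variable will be tabulated by dose group to look for gross trends over" time.

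Section 10.6 carries the grouping into individual analyses. Section 10.6.1.1: "Adverse events will be summarized by presenting, for each dose group, the number and percentage of patients having any AE". The same section summarises vital signs and ECG for each dose group. Section 10.6.3.1: "The change from baseline in neurocognitive assessment based scores will be examined by dose group", and quality of life is treated likewise.

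The dosing sections change the dose of one of those groups. Section 6.4: "Patients assigned to Group 1 (10 mg once per month [Q4W]) will have their dose increased to 45 mg once per month (Q4W"). That sentence ties the change to the next injection "following full approval of protocol Amendment 4". Sections 1.3, 4.1 and 6.2 and the synopsis agree. Baseline remains the first dose in HGT-SAN-055 (Section 4.1).

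**The concern.** Once the switch has taken place nobody receives 10 mg, yet a 10 mg column continues for every efficacy and safety variable. No rule in Section 10 splits Group 1 at the switch, renames it, or attributes events to the dose in force at onset.

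Long-term safety is the primary endpoint, and Section 4.1 describes the study as evaluating three dose levels. Section 1.3 reports that the fall in CSF heparan sulfate was greatest at the two higher doses, and justifies the increase partly by the absence of an apparent safety difference between doses. A table that files 45 mg experience under 10 mg blurs the dose comparison and weakens the long-term check on that justification. With at most 12 patients over three groups, one misfiled event visibly changes a column percentage.

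**Working it through.** **What dose group means.** Section 10 does not define it. Section 1 uses it as an assignment label that stays with the patient when the dose changes: "patients in the lowest dose group will have their dose increased to 45 mg".

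- *Assigned group (the reading that the wording favours).* The 10 mg column holds 10 mg experience up to the switch and 45 mg experience after it.
- *Dose received.* The same patients count in both the 10 and 45 mg columns, the 45 mg column includes patients pre-treated at 10 mg, and Group 1 change from baseline spans two doses.

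Either way the three column labels do not describe what the columns contain. Adverse events are counts and percentages of patients, with no exposure time at each dose.

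**How much 45 mg exposure is involved.** The protocol gives no figure to reproduce, so I bound it from its dates.

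Inputs:
- Original protocol, 21 June 2010 (synopsis): no patient can have entered this study earlier.
- Amendment 4, 3 May 2013 (Amendment 5 summary of changes): no switch can be earlier.
- Planned treatment: 48 months here after 6 in HGT-SAN-055 (Appendix 1 note).
- Lag from amendment date to full approval: not given; assumed 0 to 9 months.

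Longest possible time in this study at the Amendment 4 date: 1,047 days / 30.4375 = 34.4 months.

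For the earliest possible entrant who completes, months at 10 mg in this study are a = 34.4 + lag, and months at 45 mg are b = 48 − a. Share of time = b/48. Share of drug mass = 45b/(45b + 10a).

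| Assumed lag (months) | a, at 10 mg | b, at 45 mg | Share of time | Share of drug mass |
|---|---|---|---|---|
| 0 | 34.4 | 13.6 | 28% | 64% |
| 3 | 37.4 | 10.6 | 22% | 56% |
| 6 | 40.4 | 7.6 | 16% | 46% |
| 9 | 43.4 | 4.6 | 10% | 32% |

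These are minima at each lag, because a patient who entered later switches at an earlier study month. A switch at Month 36 from the start of HGT-SAN-055, for example, gives (54 − 36)/48 = 38%.

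**Which efficacy visits are affected.** Full testing falls at Months 12, 24, 36 and 54. In the latest case with no lag the switch comes at Month 6 + 34.4 = 40.4, so Months 12 to 36 are on 10 mg and Month 54 is on 45 mg. Month 54 remains on 45 mg for any lag shorter than 13.6 months. Patients who entered later have more visits on 45 mg.

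**The case against.** Summarising by originally assigned group is a recognised convention, and the protocol is open about the increase. On that view the fault is an imprecise label. Section 10.6.3.2 also leaves planned analyses and presentations to the SAP, and attribution rules and exposure-adjusted rates are usual SAP content. This stands in part: the absence of such detail is no fault in a protocol. But the protocol itself names the three columns in a version that also contains the switch, so a SAP that follows it inherits the mislabelling.

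Three stronger inferences are tempting, and the documents do not support them.

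- *That Section 10 was left untouched by Amendment 4.* The Amendment 4 summary of changes lists revisions to 10.1, 10.3, 10.6.1.1 and 10.6.2.1, concerning exploratory hypotheses and device analyses. What is missing is an adaptation of the dose columns to the switch.
- *That experience before and after the switch is hidden or cannot be compared.* Laboratory and antibody results are tabulated by visit, data are plotted over time, and all safety data are listed (10.1, 10.6.1.1). Onset dates, injection dates and planned doses are recorded (7.23.5.2, 6.3.2). With at most 12 patients a reader could rebuild much of this. The summary tables would still mislead.
- *That most of the 10 mg column is 45 mg time.* This holds only for an early switch. The protocol dates allow a switch after Month 40, where the share of time is 28% or less. Any total in mg would also need actual injection counts, since dosing is every 28 days, not once per calendar month.

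**Conclusion.** The inconsistency is real and lies within the current text. Followed as written, with dose group read as assignment, the plan reports adverse events and late efficacy values arising on 45 mg under 10 mg. For a Group 1 completer the misfiled period is at least about 13.6 of 48 extension months (28%) with immediate approval, about 4.6 months (10%) with an assumed 9-month lag, and longer for later entrants. In all these cases Month 54 is affected. The bounds assume entry no earlier than the original protocol date and completion of 48 months; a patient who left before approval would have had 10 mg only.

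A reader might infer that this invalidates the dose comparison or must be settled before anything else. The documents do not support that: Section 10.1 tests no prior hypotheses and the analysis is descriptive, so no error rate or sample size depends on it. It should be fixed because the tables would otherwise say something untrue about dose.

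**What to change.** Change the analysis text only; dosing is not in question.

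- In 10.1, with matching wording in the synopsis, label Group 1 as 10/45 mg. Keep assigned groups for baseline and longitudinal displays, with each patient's switch marked.
- In 10.6.1.1, tabulate adverse events by dose at onset, with patient-time at each dose. State that Group 1 patients contribute to both the 10 mg and the 45 mg periods.
- In 10.6.3, show Group 1 values before and after the switch as description only. State that dose is confounded with time and with progression of the disease, so a before-after difference cannot be read as a dose effect.

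The cost is revised wording and a few more tables, built from data already on the eCRF. The drawback is small numbers in each cell.
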